The study will compare an intervention for AAM patients versus a usual care control group. The intervention will use multimedia educational training materials to increase patients' understanding of prostate cancer (risk, screening, diagnoses and treatment), PSA-based screening (benefits, risks, harms, and guidelines), and shared decision making process (options, perceptions, preferences, actions). Patients will be randomly assigned to the intervention or control group. A battery of instruments will be applied in several intervals during the study period to collect pre-post and follow-up data. Generalized linear mixed models will be used to test our hypotheses that 1) the intervention will increase provider-patient engagement in SDM and 2) patients in the intervention arm will have higher decision confidence and satisfaction, and preference-congruent decision making than those in the control group. ANOVAs and chi-square tests will assess group differences on PCPs and patient characteristics.

2. Subject Population

Participants: During the study period we expect to recruit 200 male patients who: 1) self-identify as African American; 2) are 40-69 year old; 3) are currently a patient of a study clinical site; and 4) are able to read and understand spoken English (5th grade level). Patients will be excluded if they have 1) history of prostate cancer, or 2) medical conditions that inhibit them to complete any aspect of the intervention. Half of these participants (n=100) will be randomly assigned to the intervention arm (educational program about prostate cancer risks, screening and decision making), and the other half (n=100) will be randomly assigned to the control arm (usual care).

3. Study procedures

Project total duration is five years (April 2019 - Dec 2023). In general, we have revised and updated the study procedures, educational intervention, recruitment strategies, and assessment materials in year 1, and will begin enrollment in year 2. Assessment of the comparative effectiveness of the intervention will occur during years 2, 3 and 4 (clinical trial). Follow-up of study outcomes, evaluation of the acceptability of the intervention, and manuscripts preparation will occur in year 5.

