Face-to-face visit: This wellness visit will take place in the PCP's consultation room at the respective clinical site and will be audio-recorded after patient/PCP's consent. At the beginning of the encounter the research assistant will ask authorization to record the conversation. If the audio-recording is authorized, the research assistant will start the recording. If the audio-recording is not authorized, the research assistant will bring an evaluation form (Physician-Collaborator Patient Evaluation, Appendix 4) for the PCP to rate the conversation. Once the encounter is completed the research assistant will pick up the recorder or the respective evaluation form and will give the PCP a \$50 electronic gift card as appreciation for the time spent. Immediately after the encounter the patient will complete the post-encounter surveys (Intention-to-Screen questions, Shared Decision Making Questionnaire, and Decisional Self-efficacy – Appendix 8B) and will receive a \$40 electronic gift card as compensation for the time spent and any expenses incurred during the visit (transportation, parking, Internet and phone services, etc.).

Follow-up procedures (Visit #3): At 3-months after the medical encounter (visit #2) patients will complete brief post-intervention surveys (Prostate Cancer Knowledge, Decisional Confidence, Satisfaction with Decision, and Intention-to-Screen questions) and an additional questionnaire about the acceptability of the intervention and procedures. These surveys (Appendix 8C) may be completed online or face-to-face, as follow:

- **Online visit:** Research team will send an email (Appendix 1) to participants including a personalized link to the follow-up surveys including contact information in case that participants have questions.
- **Face-to-face visit:** These surveys will be administrated by the research team in a face-to-face meeting that will be scheduled immediately after the medical encounter (visit #2).

After completing the surveys, patients will receive a \$20 electronic gift card as compensation for the time spent and any expenses incurred during the visit (transportation, parking, Internet and phone services, etc.). Additionally, research team will check each year the medical records of each participating patient to see if they have had or not received a new PSA exam during the study period (Jan 2020-Dec 2023).

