Duration: The entire study procedures for each patient may be completed in around six months, including follow-up (Table 1). It is expected that consent and baseline survey (visit #1) will take about 15 to 30 minutes to fill out. Intervention patients will take around 30-45 minutes completing the educational program, including the pre- and post-tests. The PCP/Patient medical encounter (visit #2) will take around 1 hour according to the clinical site schedules and including time needed for patient to complete the respective surveys. Patients' follow-up assessment (visit #3) will take around 15-20 minutes.

Measures and Outcomes. Outcomes will be assessed using different measures (Appendices 4 and 8) and across different post-intervention intervals: immediately after the clinical encounter (visit #2), and at 3-month (± 15 days; visit #3). The primary outcome will be the extent to which patients and clinicians engage in SDM during the patient-clinician encounter (visit #2) following receipt of the intervention or control, evaluated using the Shared Decision Making Questionnaire (SDM-Q). Two secondary outcomes will include: 1) *patient quality of decision-making process*, assessed at baseline (visit #1), immediately after the patient-clinician encounter (visit #2), and at 3-months post intervention (visit #3) using a composite score of the following scales: Prostate Cancer Knowledge, Decisional Confidence, Decisional Self-efficacy, and Satisfaction with Decision, and 2) *Preference-congruent decision making* to examine whether patient preferences for or against receiving PSA-based screening, assessed with Intention-to-Screen questions at baseline (visit #1) and immediately after the clinical encounter (visit #2) align with care received during the subsequent 3 months (physician orders of PSA screening and actual receipt of PSA screen will be extracted from the electronic medical record). The acceptability of intervention and procedures (Tertiary outcome) will be accessed with a structured questionnaire (Appendix 8) to rate the acceptability of the enrollment process, the delivery of the intervention, and their overall satisfaction with the study that patients will complete at the 3-months follow-up (visit #3). Additionally, patients in the intervention arm will complete an evaluation of the educational intervention and the decision aid questions included in the training (Appendix 8D).

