Below is the **Study Design Schema** about the randomization of patients and assessment for both the intervention and the control arms (Figure 1) and the **schedule of activities** and measures to be completed (Table 1).

Figure 1: Study Design Schema

[figure not shown]

Table 1: Study activities and measures to be completed

Visit	Timeline	Procedure	Outcome	Measures
-------	----------	-----------	---------	----------

Visit #1 Consent & Baseline (15-60 min)	After initial contact with patient	Review/sign consent and HIPPA forms		
 • Consent form • HIPPA authorization form
		Complete baseline assessment	Secondary outcome: Patient quality of SDM	
 • Prostate Cancer Knowledge • Decisional Confidence • Satisfaction with Decision • Decisional Self-efficacy
			Secondary outcome: Preference-Congruent DM	
 • Intention-to-Screen questions • PSA screening orders and actual receipt of PSA screen, extracted from the electronic medical record
Intervention (30-45 min)	Before visit #2	Patients in intervention arm: complete training		
 • Prostate Cancer Knowledge • Intention-to-Screen questions • Decision aid questions • Evaluation of training
Visit #2 Medical encounter (approx. 1 hour)	During 3 months after visit #1 and intervention	Complete medical encounter	Primary outcome: Patient and clinicians engagement in SDM	
 • Shared Decision Making-Patient • Shared Decision Making-PCP • Intention-to-Screen questions • Decisional Self-efficacy
Visit #3 Follow-up (15-20 min)	3 months after visit #2	Complete follow-up assessment	Secondary outcome: Patient quality of DM	
 • Prostate Cancer Knowledge • Decisional Confidence • Satisfaction with Decision
			Secondary outcome: Preference-Congruent DM	
 • Intention-to-Screen questions • PSA screening orders and actual receipt of PSA screen, extracted from the electronic medical record
			Tertiary outcome: Acceptability of intervention and procedures	
 • Acceptability of Intervention • Intervention Appropriateness • Feasibility of Intervention

4. Risks

The risks to the patients as participants are minimal.

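### Does the protocol make control patients rate, at Visit 3, a training they have not yet had?

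*Protocol*

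**What the plan says.** Three places in section 3 of the protocol define the acceptability assessment at Visit 3.

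- The follow-up procedures state that "patients will complete brief post-intervention surveys (Prostate Cancer Knowledge, Decisional Confidence, Satisfaction with Decision, and Intention-to-Screen questions") and, in the same sentence, add "an additional questionnaire about the acceptability of the intervention and procedures".
- The Measures and Outcomes paragraph describes the tertiary outcome as a structured questionnaire "to rate the acceptability of the enrollment process, the delivery of the intervention, and their overall satisfaction with the study that patients will complete" at Visit 3. The next sentence is limited to one arm: "Additionally, patients in the intervention arm will complete an evaluation of the educational intervention", using Appendix 8D.
- The Visit 3 tertiary row of Table 1 lists "Acceptability of Intervention • Intervention Appropriateness • Feasibility of Intervention" with no arm label. The training row of the same table does carry one: "Patients in intervention arm: complete training".

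On timing, the educational intervention paragraph in section 3 offers controls the training only when all their study procedures are complete, which it puts at six months after enrollment. Section 5 (Benefits, Individual) places it after the intervention has been evaluated.

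On numbers, section 2 puts 100 men in the intervention arm and states that "the other half (n=100) will be randomly assigned to the control arm (usual care").

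**The concern.** The follow-up sentence has one grammatical subject for both the outcome surveys and the acceptability questionnaire. That subject must include controls for the outcome surveys. Section 1 hypothesizes that "patients in the intervention arm will have higher decision confidence and satisfaction, and preference-congruent decision making than those in the control group", and after baseline Table 1 lists Decisional Confidence and Satisfaction with Decision only at Visit 3. If the same men also complete the questionnaire, controls are asked about the acceptability, appropriateness and feasibility of a training they have not seen.

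Two explicit arm labels nearby, in the training row of Table 1 and in the Appendix 8D sentence, suggest that the authors name an arm when they mean one. Acceptability is the third of the three study aims. If half of its ratings came from unexposed men and were pooled with the rest, the summary would not describe how the intervention was received.

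**Working it through.** **Have controls had the training by Visit 3?** Table 1 puts Visit 2 within 3 months after Visit 1. Visit 3 follows 3 months later, ± 15 days. The latest Visit 3 is therefore about 3 + 3 + 0.5 = 6.5 months after enrollment, slightly past the six-month mark given for control training. The governing condition is completion of all procedures, and Visit 3 is one of them, so control training comes after Visit 3. This part of the concern is right.

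**How many men are involved on the literal reading?** The planned allocation gives 100 / 200 = 50% before dropout.

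**Does the protocol name the arm whenever it means one arm?** The literal reading depends on this, and it fails in four places:

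- The Intervention paragraph of the opening summary uses an unqualified subject for surveys at baseline, during the training and at follow-up. The middle set can only be taken by men who receive the training.
- The Visit 1 text in section 3 pays patients a \$40 gift card after consent, surveys and training. At that point only the intervention arm has training to complete.
- The educational intervention paragraph emails the training link to participants, with no arm in that sentence, although the paragraph as a whole concerns the intervention arm.
- The follow-up sentence calls the Visit 3 surveys post-intervention, although controls have had no intervention.

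Read as strictly as the Visit 3 sentence, the first of these would have controls take the training's pre- and post-tests, which nobody would conclude. The wording is loose throughout, so a missing arm label carries little information.

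**Where would routing by arm be specified?** It would be in the questionnaire itself (Appendix 8) or in Figure 1, which is introduced as showing assessment for both arms. Neither is shown. Online follow-up uses a personalized link for each participant, and face-to-face surveys are administered by the research team. Either route allows items to be skipped by arm.

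**What would the data look like in the worst case?** Suppose controls did answer every item.

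- Reported by arm, the intervention-arm mean rests on at most 100 men, with a 95% half-width of 1.96 / √100 = 0.196 SD. It rests on the same men if controls were never asked. At an assumed 80% retention it is 1.96 / √80 = 0.219 SD in both cases.
- Pooled over equal arms, the mean would be 0.5 × (intervention mean) + 0.5 × (control mean). It would differ from the intervention-arm mean by half the difference between arms. The apparent half-width would be 1.96 / √200 = 0.139 SD (0.155 SD with 160 men), a spurious gain. The protocol states no such pooling.

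An arm label would therefore leave the usable estimate and its precision unchanged.

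**The case for a change.** The strongest case for acting is that who completes a measure is a matter of data collection, which this protocol sets out itself and cannot leave to an SAP. No later analysis can make an unexposed man's rating informative. The word that opens the Appendix 8D sentence also suggests an intervention-arm extra on top of a questionnaire meant for everyone. The correction would cost only a phrase and some survey skip logic.

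Much of this stands. The visible text is ambiguous, and control ratings of unseen training would have no value for the third aim. It is also fair that some of the questionnaire is meant for everyone, since controls can validly rate the enrollment process, the study procedures and their overall satisfaction. That is itself a good reason for a sentence covering both arms, and it weakens the inference that the intervention items were meant for controls too.

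The argument does not show a consequence. Surplus answers from controls would be set aside, at the cost of a few minutes of respondent time. The claim that all three measures in the tertiary row concern only the training rests on their titles, because the items are not shown.

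**Conclusion.** No change to the plan is called for. This is a missing arm label on a tertiary process outcome, of a kind that the survey build or the analyst supplies as a matter of course. At its largest it concerns 100 of 200 planned respondents on the three intervention-rating measures and the delivery items. The intervention-arm estimate and its precision are the same either way, and no primary or secondary result depends on it.

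The conclusion assumes that intervention ratings are reported for the intervention arm and are not pooled. Nothing in the protocol says otherwise, and assignment is known for each patient. It also allows for Figure 1 and Appendix 8, which may already route the items and could not be checked. A stated plan to pool these ratings across arms would alter the conclusion, and the protocol contains none.

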Study Outcomes: The primary outcome will be the extent to which patients and clinicians engage in SDM during the medical encounter following receipt of the intervention or control. Two secondary outcomes include *Patient quality of decision-making process* (knowledge, decisional confidence, self-efficacy, and satisfaction) and *Preference-congruent decision making* to examine whether patient preferences for or against receiving PSA-based screening align with care received (actual receipt of PSA test, extracted from the electronic medical record).

Subjects: 200 African American men, 40-69 years old, with NO diagnostic of prostate cancer, who are receiving primary care (annual physicals and preventive care) at the clinical sites during the project period (2020-2023).

Intervention: Patients will be randomly assigned to receive a 30-45 minute online educational intervention (n=100) or control group (n=100). Patients receiving the training will learn about prostate cancer (risk, screening, diagnoses and treatment), PSA-based screening (benefits, risks, harms, and guidelines), and SDM process (options, perceptions, preferences, actions). In order to measure the application of the SDM process in the clinical setting (primary outcome), patients will discuss the PSA test with their respective primary care provider (PCPs) during a medical wellness visit (annual checkup). The conversation will be audio-recorded, after patient/PCP's assent, and evaluated to identify the application of the different components of the SDM process. If the audio-recording is not authorized, the patient and PCP will complete an evaluation survey about the encounter. Patients will complete online surveys at enrollment (baseline), during the training (pre-post test), and 3-months after medical encounter (follow-up).

Enrollment: Searches in electronic medical records will be conducted to pre-screen and invite (mail, calls, and emails) eligible patients and their respective PCPs to join the study. Patients will complete in-person or online consent and HIPPA authorizations. PCPs' will complete an online baseline survey and provide implicit consent to join the study.

RESEARCH PROTOCOL

Study Title: Fostering Shared Decision-Making about Prostate Cancer Screening among Clinicians and African American men

1. Study aim, background, and design

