- For those completing the visit face-to-face, and based on participant preferences and time and transportation constraints, the meeting could be scheduled at the private offices of research personnel, at the respective clinic, or in a specific place chosen by the patient where privacy may be preserved. In this case, the consent (Appendix 6A) and HIPPA (Appendix 7A) forms will be completed on paper and signed copies will be given to participants to keep.
- For those completing the visit online, the consent will be presented on a set of questions and short answers extracted from the consent form (Appendix 6B) and a link to the entire consent will be available so participants can read and save the entire document before continuing with the consent process. The online consent requires electronic signature for the consent and HIPPA (Appendix 7B) authorization. Patients can sign the documents by signing their name using the finger, mouse or stylus pen.

After completing the consent, surveys and training, patients will receive a \$40 electronic gift card as compensation for the time spent and any expenses incurred during the visit (transportation, parking, Internet and phone services, etc.)

Educational intervention procedures (online training): Patients randomly assigned to the intervention arm will complete an online educational program (Appendix 9) to enhance knowledge about prostate cancer and risks, and application of shared decision making (SDM) skills. Patients will complete the training immediately after enrollment and baseline (Visit #1). Research team will send an email (Appendix 1) to participants including a personalized link to the training and respective surveys (Prostate Cancer Knowledge, Intention-to-Screen questions, Evaluation of Training and Decision Aid Questions, Appendix 8D), and

contact information in case that participants have questions or need help to navigate the site. Patients in the control arm will be given instructions to complete the training once the entire study procedures are completed (6-months after enrollment).

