Patients and Primary Care Providers (PCPs) medical encounter (Visit #2): In order to measure the application of the SDM process during the clinical setting, patients will discuss the PSA screening with their respective primary care provider (PCP) during a medical wellness visit (annual checkup). Each week, research team will send a reminder (email and/or phone call) to all enrolled patients having scheduled wellness visits in that week, and their respective Primary Care Providers (PCPs).

This visit may be conducted online or face-to-face, as follow:

Online visit: This wellness visit will take place online. The clinical sites have available telehealth services including Zoom videoconference that are HIPPA compliant. An email to schedule the virtual visit (Appendix 1) will be send by Research team to the respective Patient/PCP. Patients who prefer this option will receive instructions on how to proceed. At the beginning of the meeting, the patient and PCP will confirm that they are in a place where privacy may be preserved and that authorize to audio-record the encounter. If the audio-recording is authorized, the research team member will start the recording. If the audio-recording is not authorized or possible, after the encounter the PCP will rate the conversation using the online evaluation form (Physician-Collaborator Patient Evaluation, Appendix 4) and the-patient will complete the online post-encounter surveys (Intention-to-Screen questions, Shared Decision Making Questionnaire, and Decisional Self-efficacy – Appendix 8B). Once the encounter and evaluations are completed the PCP and patients will receive the respective electronic gift card (\$50 and \$40) for the time spent and any expenses incurred during the visit (transportation, parking, Internet and phone services, etc.).

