Participants considering the interventions offensive, risky, embarrassing, or not appropriated to their cultural beliefs, may stop participating at any time. No additional information about these participants will be collected when they stop participating.

Codes will be assigned to each patient participating so it is possible to match pre-tests and post-tests with real performance during the clinical encounters but at the same time protect patients' privacy. Codes will be assigned by research personnel once the consent form is signed (visit #1) and will be recorded, instead of names, in all study records (surveys, medical encounter, intervention, etc.). Names, address, email and phone numbers will be used by research team only to contact the participants. Qualtrics, the software to capture and store project data, uses Transport Layer Security (TLS) encryption for all transmitted Internet data and has the functionality to ensure the confidentiality of survey results. Microsoft OneDrive, which uses encryption for files (at-rest and in-transit), was approved by Xavier Office of Technology Administration to share project files among the research team.

The patient informed consent process includes authorization to audio-record the clinical encounter and the HIPAA authorization to access health records. Only contact information (name, address, phones and email) and PSA screenings (having or not PSA screening) will be extracted (entered to a digital file) from the medical records and patient will be identified with the respective code assigned. Only authorized research personnel (listed in the IRB application) will have access to the medical records. Audio recording of the clinical encounter, where PSA screening is discussed, will be rated by research personnel. Audio files will be password protected, kept in secured computers for 6 months after the medical encounter (visit #2), and then deleted. No copies of these audios will be made. However, clinicians participating in the medical encounter may write a note into the respective patient health record about the decision of ordering or not the PSA test as part of the decision making process.

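### Encounter recordings are rated by research personnel with no masking to arm, and it is unclear whether that rating or the SDM-Q is the primary measure

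*Protocol*

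**What the plan says.** **Who rates.** Section 4, under the procedures to minimize risks: "Audio recording of the clinical encounter, where PSA screening is discussed, will be rated by research personnel". No masking, independence or division of tasks is described.

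**Who knows the arm.** Section 3, on the educational intervention: "Research team will send an email (Appendix 1) to participants including a personalized link to the training and respective surveys". This goes to intervention patients right after baseline; controls are offered the training only when their study procedures are over.

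**Who starts the recording.** At an online Visit #2, "the research team member will start the recording"; face to face, "the research assistant will start the recording".

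**What the code does.** Section 4 has research personnel assign each patient a code at consent. It replaces the name on every study record, including the surveys, the medical encounter and the intervention. Its stated purposes are matching records and privacy. Project files are shared within the team on OneDrive.

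**What the rating is for.** The synopsis (Intervention): "In order to measure the application of the SDM process in the clinical setting (primary outcome), patients will discuss the PSA test". The recorded conversation is then "evaluated to identify the application of the different components of the SDM process". An evaluation survey applies if recording is not authorized.

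**The competing definition.** Section 3, Measures and Outcomes, has the primary outcome "evaluated using the Shared Decision Making Questionnaire (SDM-Q"). Table 1 lists patient and PCP versions of an SDM measure at Visit #2 and no observer rating.

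**Retention.** Section 4 keeps audio files for 6 months after Visit #2, then deletes them. No copies are made.

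**The concern.** Deciding from a recording how far each SDM component was applied is a subjective judgement. A rater who knows that a man was trained may hear more engagement than one who does not. Such an error differs by arm, and enrolling more patients does not reduce it.

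Patients know whether they took the training before the visit, so their own questionnaire answers cannot be masked. The audio rating is the measure of SDM at the encounter that could most readily be made without knowledge of arm, and the procedure as written does not secure that. Who rates, and what they may know, is settled while the trial runs; an analysis plan cannot restore masking afterwards. Deletion of the audio also rules out masked re-rating after six months.

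**Working it through.** The protocol gives no alpha, power, effect size, SD or bias figure, so there is no stated number to reproduce. The check has two parts.

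**A. The text set side by side**

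1. *Could a rater learn the arm?* The link-sending team knows who was trained. The same patient code appears on the encounter record and the intervention record, and files are shared within the team. A coded recording can therefore be traced to arm by anyone with access to both. Nothing stated prevents a rater from having that access.
2. *Does starting the recorder reveal the arm?* No. It shows contact with the patient and PCP, not knowledge of allocation.
3. *Does the rating feed the primary outcome?*
   - Synopsis: the recorded discussion measures the primary outcome, and the survey is the fallback.
   - Section 3, online visit: the PCP form and the patient surveys are both described only for encounters where recording is not authorized or not possible. Read literally, a recorded online encounter yields no Visit #2 measure except the audio rating.
   - Section 3, face-to-face visit: the PCP form is used only when recording is refused, but the patient surveys follow the encounter without that condition.
   - Measures and Outcomes and Table 1: the questionnaire measures the primary outcome, and no audio rating is listed.

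   These statements do not agree, so the role of the rating is unsettled.

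**B. Illustration of size (assumptions, not protocol figures)**

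Inputs: 100 patients per arm (synopsis). Assumed: two-sided alpha 0.05, SD = 1, true effect zero, and a differential rating shift of b SD toward the intervention. Because some encounters will not be recorded, 50 rated per arm is shown as well.

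Formulas (Φ is the standard normal distribution function):
- shift in the test statistic: s = b × √(n/2)
- false-positive rate = [1 − Φ(1.96 − s)] + Φ(−1.96 − s)

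| b (SD) | s, n = 100 | Rate, n = 100 | s, n = 50 | Rate, n = 50 |
|---|---|---|---|---|
| 0 | 0 | 5.0% | 0 | 5.0% |
| 0.1 | 0.71 | 10.9% | 0.50 | 7.9% |
| 0.2 | 1.41 | 29.3% | 1.00 | 17.0% |
| 0.3 | 2.12 | 56.4% | 1.50 | 32.3% |

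Example, b = 0.2 and n = 100: s = 0.2 × √50 = 1.41; 1 − Φ(0.55) = 0.2926; Φ(−3.37) = 0.0004; total 0.293.

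For scale, under the same assumptions the difference detectable with 80% power at 100 per arm is (1.96 + 0.84) × √(2/100) = 0.396 SD. A shift of 0.2 SD is about half of that.

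**The case against.** A reader might infer that the people who email training links and attend visits are the ones who rate the audio, and that raters therefore know the arm. The protocol does not say so. It uses collective terms (research team, research personnel, research assistant). A team member with no part in allocation could rate coded audio and comply with every sentence. In the face-to-face description the assistant starts the recorder and collects it afterwards; nothing says the assistant stays for the conversation. What stands is narrower: the roles are not separated, and the coding and file sharing leave a path from recording to arm.

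It can also be said that the primary outcome is the SDM-Q, so masking of raters touches only a supporting measure and the larger route to bias is self-report by patients who know their arm. That is right if Measures and Outcomes and Table 1 govern. It is not right if the synopsis and the online-visit text govern, since there the surveys replace the rating only when there is no recording.

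The percentages follow mechanically from assumed shifts, and nothing in the protocol supports any particular value. Finally, Figure 1 and the appendices are not shown, so rating detail there could not be checked.

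**Conclusion.** The point holds in this form: a subjective rating of the encounter is given to research personnel, the stated procedure neither masks them to arm nor separates them from staff who know it, and the patient code does not conceal arm. It does not show that raters will know the arm or that the ratings will be biased.

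The consequence depends on a question that the protocol leaves open. If the audio rating is primary, the exposure is on the main comparison; if the SDM-Q alone is primary, it is on a supporting measure. The false-positive rates of about 11% to 56% (100 rated per arm) or 8% to 32% (50 rated per arm) are illustrations for assumed shifts of 0.1 to 0.3 SD, not estimates for this trial.

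The change is worth making because it is inexpensive and because the option of masked re-rating ends when each file is deleted.

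**What to change.** In Section 4, and again under Visit #2 in Section 3, state that:

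- recordings carry an arm-neutral code that raters cannot link to the intervention records;
- raters are existing team members who had no role in allocation, in sending training links or at that visit;
- ratings are locked before the six-month deletion of each file and before raters can see the allocation;
- raters note when the conversation itself reveals the arm.

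Separately, reconcile the synopsis, the online-visit and face-to-face text, Measures and Outcomes, and Table 1 on whether the audio rating or the SDM-Q is the primary measure. State which Visit #2 instruments are completed when the encounter is recorded.

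Cost: about a paragraph of text, division of tasks within the present team, and minor scheduling. Masking will be imperfect when a patient mentions the training on the recording, which is why raters should note it.
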